Type I error. The significance level will be 0.025 for the 1-tailed noninferiority tests for the primary outcome and for each set of the secondary outcomes, and 0.05 for each of the 2-tailed superiority tests for tertiary outcomes (i.e., no adjustment for multiple testing for tertiary outcomes).

Our primary hypothesis is that HES 130/0.4 is noninferior to standard care effects on **mean urinary NGAL** measured within one hour of arrival to ICU and 24 following completion of surgery. We a priori define the noninferiority delta for urinary NGAL as a ratio of geometric means (since NGAL data are expected to be lognormal) of 1.15, for an effective delta of 15% of the control group mean. [Note: for this and other outcomes, if the data are non-normal, a log-transformation will be attempted and the treatment effect (if normal on the log-scale) will be summarized as the ratio of geometric means, equivalent to the difference in means of the log-transformed data.] As noted below under “Continuous outcomes measured over time (Primary and Secondary Aims)”, we will assess the treatment effect for the primary outcome in the context of a linear mixed model which allows us to simultaneously assess the effect across the collapsed time points if there is no group-time interaction, or else at specific times if there is an interaction detected. We will conduct tests for noninferiority using treatment effect estimates from the linear mixed model and applying 1-tailed t-tests for noninferiority as described in Mascha and Sessler (2011) [Mascha EJ, Sessler DI: Statistical grand rounds: Equivalence and noninferiority testing for regression models and repeated measures designs. Anesth Analg 2011; 112: 678–87], and with t-statistic as follows:

$$T_{NI} = \frac{\hat{\beta}_1 + \delta}{SE_{\hat{\beta}_1}}, \text{ where } \hat{\beta}_1 \text{ is the estimated treatment effect with standard error}$$

$SE_{\hat{\beta}_1}$ and noninferiority delta of δ .

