Continuous outcomes measured over time (Primary and secondary aims). For the primary outcome (urinary NGAL) and each of the secondary continuous outcomes which are measured over time (e.g., at baseline, within one hour of arrival to ICU following surgery, and 24 hours following completion of surgery), we will assess the treatment effect of HES 130/0.4 versus standard care using linear mixed effects models (with patient as random effect), adjusting for the baseline value of the outcome and any baseline variables for which balance among the randomized groups was not achieved through randomization. We will adjust for the baseline value of the outcome for efficiency, i.e., to obtain a smaller standard error for the estimate of treatment effect to the extent that the baseline value is correlated with the later time points, regardless of baseline balance. An unstructured within-subject correlation structure will be employed, estimating a distinct correlation parameter for each pair of post-baseline measurement times.

If the treatment group-by-time interaction is significant ($P < 0.15$), the treatment effect for a particular outcome will be assessed at each of the post-baseline time points measured, using a Bonferroni (or other appropriate) correction for multiple comparisons procedure if comparing groups at specific time points. Similarly, correction to the significance criterion will be made in all analyses below when comparing multiple times, as appropriate.

Ordinal outcome. Groups will be compared on the ordinal outcome of the RIFLE criteria (Secondary Aim 1) using proportional odds logistic regression, adjusting for baseline imbalance

as needed. We will assess noninferiority using the approach described above for the primary outcome, where $\hat{\beta}_1$ is the estimated treatment effect in the form of a log-odds ratio.

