Time to event outcomes. Randomized groups will be compared on time to event outcomes including duration of mechanical ventilation, duration of stay in the intensive care unit, and duration of hospital stay using Cox proportional hazards regression models adjusting for any baseline imbalances covariables. For these models the outcome will be time to experiencing the event while alive, i.e., time to removing the ventilator, discharge from the ICU and discharge from the hospital. Patients who die before the event occurs will be listed as failures (i.e., no event) and censored at a time just beyond the last observed event for any patient. Ignoring the deaths or censoring at the time of death may introduce bias.

Binary outcomes. Groups will be compared on binary outcomes, including in-hospital cardiac, renal, infection, or neurologic morbidity, and overall major morbidity (including death), using either logistic regression (to adjust for baseline imbalance as needed) or Pearson chi-square or Fisher's exact test, as appropriate. However, the study is not powered for assessing binary outcomes, and these analyses particularly will be interpreted with caution (whether significant or not).

For all analyses, confidence intervals for the estimated treatment effect will be provided, and these, along with the point estimates of treatment effect, will be emphasized in our reporting. SAS statistical software (Carey, NC) and R software version 2.8.1 for Windows (The R Foundation for Statistical Computing, Vienna, Austria) will be used for all statistical analyses.

Missing data. If primary or secondary outcome data are missing we will use multiple imputation of outcome values based on all available data before the time point of interest. As a secondary analysis we will conservatively assign the worst observed value for the given time point across all patients to an HES patient and best observed value to a control patient. If there is a non-trivial amount of missing outcome data we will also conduct sensitivity analyses on various forms of imputation (from none at all to full multiple imputation). However, we will work hard to avoid missing outcome data. If baseline data not included in the analyses are missing we will simply describe the missingness.

Sensitivity analyses. We will conduct a sensitivity analysis for the primary outcome that adjusts for time on CPB, length of surgery and intraoperative hypothermia.

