Sample size is based on assessing the noninferiority of HES 130/0.4 to 5% albumin on the primary outcome of urinary NGAL. In patients undergoing cardiac surgery, Koyner et al (2012)²⁹ observed median [quartile] urinary NGAL values of 28.3 (13.5–82.9) in patients who did not progress to renal failure and 72.1 (11.4–495.6) in patients who progressed to renal failure. Assuming that NGAL values follow a log-normal distribution as in previous studies, we can use the above observed quartiles to estimate the mean, standard deviation and coefficient of variation (CV) for the above groups, yielding CV of 2.3% and 50%, respectively. Assuming for the current study a coefficient of variation between these values, or 25%, we would need 52 patients per group (total of 104) to have 90% power at the 0.025 significance level to be able to claim noninferiority of HES to albumin using a noninferiority delta of a ratio of geometric means of 1.15. These calculations assume no treatment-time interaction and therefore no Bonferroni correction for comparing groups at each of two time points within an outcome. Based on the above calculations, a sample size of 110 would suffice for a study with no interim monitoring. **Adjusting for the interim monitoring at each one-sixth of the total, a maximum sample size of 130 patients are required. Allowing for 5 potential dropouts and 5 pilot patients (which will not be included in the analyses), we will plan for a potential total of 140 patients.**

STUDY PROCEDURES

Quality Assurance

The major components of quality assurance will be staff training, the standardization of data collection, entry, and processing, and ongoing monitoring to ensure timeliness and accuracy of study data. All study protocols and forms will be compiled into two operations manuals (one for the clinical sites and one for data management) that will be revised as necessary. A clinical reference manual will be created and will include administration and scoring criteria, specific testing instructions and inclusion and exclusion criteria for diagnosis and study ascertainment. This manual will also contain copies of test forms and will be available to all study personnel from a password-protected web site. The current manual for data management will be made easily available to data management personnel and used for continued training. This manual will include a question-by-question written script for interviewing purposes.

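### The quoted NGAL quartiles imply CVs of about 230% and 5,000%, not 2.3% and 50%, so the 25% planning CV, and the power and sample sizes built on it, have no stated support

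*Combined protocol and SAP*

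**What the plan says.** In the combined protocol and SAP, Sample size calculations (Aim 1) takes its spread from one cited cohort of cardiac surgical patients, with median and quartiles "urinary NGAL values of 28.3 (13.5–82.9) in patients who did not progress to renal failure and 72.1 (11.4–495.6"; the second set belongs to patients who did progress. Assuming log-normal values, it reports the result as "yielding CV of 2.3% and 50%, respectively. Assuming for the current study a coefficient of variation between these values, or 25" percent. From that CV and a noninferiority margin of 1.15 for the ratio of geometric means, "we would need 52 patients per group (total of 104) to have 90% power at the 0.025 significance level". The section then gives 110 as enough without interim looks and says that, with looks at every sixth of the total, "a maximum sample size of 130 patients are required".

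Two features of the planned analysis bear on the effective variance. Under Type I error, the mixed model is meant to "simultaneously assess the effect across the collapsed time points if there is no group-time interaction". Under Continuous outcomes measured over time, the plan says "We will adjust for the baseline value of the outcome for efficiency". The sample size section touches on this only by noting that "These calculations assume no treatment-time interaction and therefore no Bonferroni correction". It states no correlation and no variance reduction. No other source for the NGAL spread appears in the documents.

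**The concern.** Quartiles of 13.5 and 82.9 differ six-fold, and 11.4 and 495.6 differ more than forty-fold. Neither is compatible with a CV of a few percent or of 50%. If the percentages are wrong, the choice of 25% as a value in between loses its only justification.

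At stake is the power of the single confirmatory test. If the true spread is near the cited one, the trial would usually fail to show noninferiority at 1.15 even for an equivalent product, and a reader who relied on the stated 90% would misjudge what such a failure means.

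**Working it through.** **Inputs.** From Sample size calculations (Aim 1): the two sets of quartiles, log-normality, CV 25%, margin 1.15, 90% power, 52 per group, maximum 130 (65 per arm). From Type I error: one-sided 0.025. Assumed, because it is not stated: true ratio 1.0.

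**1. CVs from the quartiles.** For a log-normal variable, log-SD s = ln(Q3/Q1)/(2 × 0.6745) and CV = √(exp(s²) − 1).
- No progression: s = ln(82.9/13.5)/1.349 = 1.815/1.349 = 1.345; CV = √(exp(1.810) − 1) = 2.26, about 230%.
- Progression: s = ln(495.6/11.4)/1.349 = 3.772/1.349 = 2.796; CV = √(exp(7.819) − 1) = 49.9, about 5,000%.

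The digits 2.3 and 50 are reproduced as ratios, so the likely cause is a percent sign attached to a ratio.

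**2. Where 25% lies.** CV 25% means s = √ln(1 + 0.25²) = 0.246. The smaller derived CV is 2.26/0.25 = 9.0 times larger. In quartile terms, CV 25% implies Q3/Q1 = exp(1.349 × 0.246) = 1.39; the quoted ratios are 6.1 and 43.5.

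**3. The plan's 52, taking CV 25% as given.** n per group = 2s²(1.960 + 1.282)²/(ln 1.15)² = 2 × 0.0606 × 10.51/0.01953 = 65.2, so 66 (67 with the t distribution). Power by the noncentral t is 82% at 52 per group and 84% at 55 per group (the total of 110). The stated 52 is not reproduced from the stated inputs. At least two departures give it:
- a variance reduction of about 20% (52/65.2 = 0.80);
- 80% power with 0.25 used directly as the log-SD, which gives exactly 52 by the t calculation.

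The documents do not say which, if either, was used.

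**4. Power at the maximum of 130, CV 25%.** With 65 per arm, a fixed design gives about 89%. Using the p-value boundaries printed in Table 3 (first safety boundary taken as 0.0004), power is about 89% if the futility boundary is non-binding and about 83% to 84% if it is obeyed.

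**5. Scenarios at 65 per arm, fixed design.**

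| Assumed spread | log-SD | Power |
|---|---|---|
| Lower cited spread, from lower half of the quartile range, ln(28.3/13.5)/0.6745 | 1.10 | about 11% |
| Same, from upper half, ln(82.9/28.3)/0.6745 | 1.59 | about 7% |
| log-SD 1.345 with an assumed 75% of variance removed | 0.673 | about 22% |
| CV 50%, s = √ln(1.25) | 0.472 | about 39% |

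Getting from 1.345 to the planned 0.246 would require removing 1 − (0.246/1.345)² = 97% of the variance.

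**The case against.** The strongest defence is that the cited spread is not this trial's spread. The cited cohort concerns progression of acute kidney injury, whereas this trial enrols elective valve patients and excludes those with creatinine above 1.6 mg/dL. Baseline adjustment and two pooled post-baseline samples would also reduce the effective variance. Both points stand, and they are why the table above shows scenarios. A reader might infer that the trial's actual power is 8% or so; the documents do not support that, because they do not give the spread in its own population. Nor do they support 25%: they cite no narrower source and state no correlation, and a 97% reduction would be needed.

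A reader might also infer that 52 per group proves a hidden variance factor from averaging the two time points. That is one explanation among several, and the sample size text mentions none.

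A third tempting inference is that Table 3 is unaffected and can be kept as it is. Its boundaries do not depend on the CV. However, Interim monitoring analyses states a gamma of −5 for alpha spending, which at 0.025 gives cumulative spend of 0.0002, 0.0007, 0.0019, 0.0046 and 0.0108 at the first five looks. Table 3 prints 0.0004, 0.001, 0.003, 0.006 and 0.013, which fits a gamma of −4. That is a separate matter to reconcile.

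Finally, the plan promises that "confidence intervals for the estimated treatment effect will be provided, and these, along with the point estimates of treatment effect, will be emphasized". That limits the harm to interpretation, but it does not make the stated power correct.

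**Conclusion.** The arithmetic is wrong as written. The CVs are understated 100-fold, and the 25% does not lie between the values that are said to justify it. This rests only on the plan's own quartiles and its log-normal assumption. It follows that the 90% power and the totals of 104, 110 and 130 have no stated support.

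It does not follow that 90% is far out if CV 25% were true: the design would then have about 83% to 89% at 130. What lacks a basis is the 25% itself. A smaller, separate gap is that 52 per group and 110 in total do not follow from the stated inputs, which call for 66 to 67 per group. How low the power is depends on a spread that the documents do not give; the scenarios run from about 7% to 39% and all assume a true ratio of 1.0.

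**What to change.** 1. Correct the two CVs to about 230% and 5,000%.
2. Replace 25% with a log-SD consistent with the quoted quartiles, or cite a source for a narrower one in elective patients. State any correlation assumed for baseline adjustment and for pooling the two time points.
3. Recalculate and restate the power at 130 for margin 1.15, both for a fixed design and through the group-sequential boundaries, once the alpha spending in Table 3 and its text have been reconciled. Show how 52 (104) and 110 follow from the stated inputs, or correct them.
4. If 130 is kept, say that the test at 1.15 is underpowered under the cited spread.

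The cost is protocol and SAP wording plus a recalculation, and probably a much less favourable stated power. No study procedure changes, and enlarging the trial is not part of this fix.

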Appendix 1.

Diagnostic criteria for risk of kidney dysfunction

Category	Definition (serum creatinine criteria)	Definition (urine output criteria)
Risk (RIFLE-R)	Increase in serum creatinine x 1.5 from baseline	Less than 0.5 mL/kg/hr for more than 6 hrs
Injury (RIFLE-I)	Increase in serum creatinine x 2 from baseline	Less than 0.5 mL/kg/hr for more than 12 hrs
Failure (RIFLE-F)	Increase in serum creatinine x 3 from baseline	Less than 0.3 mL/kg/hr for 24 hrs or anuria for 12 hrs
Loss (RIFLE-L)	Complete loss of kidney function > 4 weeks	
End stage (RIFLE-E)	End-stage kidney failure > 3 months	

